# 4.1.5. Fractional Exhaled Nitric Oxide (FeNO)

FeNO (Appendix V) will be measured pre-bronchodilator using the NIOX VERO® (Circassia Pharmaceuticals Inc, Morrisville, NC, USA, License number 98844). Participants will be seated upright and given the mouthpiece of the NIOX VERO®. Participants will be instructed to breathe out fully, then bring the mouthpiece to their lips to create a seal around the mouthpiece. Participants are then asked to inhale deeply to total lung capacity, then exhale slowly and completely into the mouthpiece.

# 4.1.6. Multi-Detector Computed Tomography (MDCT)

Thoracic low dose MDCT will be performed with the same inhalation breath-hold volume and maneuver ( $N_2$  gas only) used for MRI to obtain participant-specific high resolution images of lung anatomy (tissue structure and airway morphology). CT imaging will be performed using an Aquilion ONE CT scanner (Canon Medical Systems USA, INC., Tustin, CA, USA) or a Lightspeed VCT CT scanner (General Electric, Waukesha WI, USA) at either Robarts Research Institute in London, Ontario or at University Hospital, located next door to Robarts Research Institute. Participants will be scanned in the supine position and during inspiration breath-hold after inhaling 1L of  $N_2$  in order to match CT and MRI breath-hold volumes and anatomy.

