# 4.1.3. Pulmonary Function Tests

Full pulmonary function tests including spirometry (Appendix I), plethysmography and diffusing capacity of carbon monoxide (DL $_{\rm CO}$ ) (Appendix II) will be performed on all participants according to ATS guidelines. MedGraphics Elite Series, MedGraphics Corporation. St. Paul, MN USA and/or nDD EasyOne Spirometer, nDD Medical Technologies Inc. Andover, MA USA will be used. All measurements will be performed in the Pulmonary Function Laboratory at Robarts Research Institute. Lung clearance index (LCI) is a marker of overall ventilation inhomogeneity within the lung derived from the multiple breath nitrogen washout (MBNW) test (Appendix III). Participants breathe normally into a mouthpiece connected to a device, the NDD EasyOne Pro Lab for approximately 3-5 minutes.

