Xe dissolved phase MRI data will be reconstructed using a re-gridding method. The following ratios will be determined by the area-under-the curve obtained from spectroscopy: red-blood-cell to alveolar membrane ratio (RBC:membrane); RBC to gas ratio (RBC:gas); and the membrane to gas ratio (membrane:gas). Spectroscopic signals will be used to reconstruct perfusion and alveolar membrane maps.

Seven-day, 14-day and 1-year reproducibility of Xe MRI measurements will be determined using the coefficient of variation and intraclass correlation coefficients (ICC). The changes in regional VDP will be evaluated for all participants after 2 years pre- and post-salbutamol.

We will evaluate Pearson correlations for MRI measurements (VDP, TCV) with CT (WA%), spirometry and plethysmography measurements to determine whether structure relates to function (and *vice versa*). We will also evaluate the relationship between sputum, biopsy, CT and MRI measurements. Significant differences in Pearson correlations will be determined using 95% Confidence Intervals (CI). To evaluate agreement between measurements, Bland-Altman plots will be generated to show the differences between WA% and He VDP with Xe VDP.

Univariate and multivariate regression models will also be used and adjusted for confounders to assess correlations of imaging measurements with dyspnea score, and asthma control measures for a better understanding of the relationship between imaging and established/validated clinical measurements of asthma. We will also examine the relationship between clinically defined asthma severity and imaging. In each of these models, we will employ a forward stepwise selection modeling process to maximize the

DATE: November 15, 2024

efficiency, while maintaining the validity of the modeling process. We will select only those covariates with a p-value of 0.25 or less and include only those variables that have a p-value of 0.2 or less in the final model. From these models, we will determine the total  $R^2$  values as well as partial  $R^2$ . The Holm-Bonferroni correction will adjust for multiple comparisons.

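### The WA% correlations in section 8 carry no term for which of two CT scanners was used; reporting scanner-adjusted results beside them would close a possible source of dilution or artefact

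*Protocol*

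**What the plan says.** Section 4.1.6 of the protocol states that "CT imaging will be performed using an Aquilion ONE CT scanner (Canon Medical Systems USA, INC., Tustin, CA, USA) or a Lightspeed VCT CT scanner" is acceptable, in either of two neighbouring buildings. The synopsis and section 6.6 repeat this. None of these places says how a participant comes to be scanned on one machine or the other, and none describes a comparison between the two.

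The visit schedule in section 4.1 lists CT in the V1 column only.

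Section 8 sets the structure-function analysis: "We will evaluate Pearson correlations for MRI measurements (VDP, TCV) with CT (WA%), spirometry and plethysmography measurements to determine whether structure relates to function". On inference it adds: "Significant differences in Pearson correlations will be determined using 95% Confidence Intervals (CI". The scanner is not mentioned.

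Covariate adjustment appears in section 8 only for a different analysis: "Univariate and multivariate regression models will also be used and adjusted for confounders to assess correlations of imaging measurements with dyspnea score" and asthma control. No confounder is named there, and entry is by p-value: "We will select only those covariates with a p-value of 0.25 or less".

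**The concern.** WA% and VDP are correlated across participants, and each participant contributes a single WA% value from a single scanner. Any systematic difference between the machines is therefore wholly a between-participant difference and passes straight into the correlation; repeat scans cannot average it out.

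Two consequences are possible. An offset unrelated to VDP adds noise to WA% and shrinks a true correlation. If VDP also differs between the scanner groups, the two differences add a covariance with no lung relation behind it, and this can push the correlation in either direction.

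These correlations matter because CT is one of the means by which the second objective and second hypothesis set out to validate 129Xe MRI. Without a scanner term, a reader of the results cannot tell a structural relation from an equipment one.

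**Working it through.** **Inputs from the protocol.** Two CT scanners (section 4.1.6), CT once at V1 (section 4.1), Pearson correlation with 95% confidence intervals (section 8), and 200 participants with asthma (section 4.3). I take n = 200 as the number with evaluable CT and MRI. The protocol has no power or sample-size derivation for these correlations, so there is no stated figure to reproduce.

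**Assumed inputs.** The protocol gives none of these:
- p: share of participants on the second scanner, taken as 0.5, with 0.2 as a check
- d: scanner offset in WA%, in within-scanner SD
- e: difference in mean VDP between the scanner groups, in within-group SD

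**Model.** Let g = 1 for the second scanner and 0 for the first. Observed WA% is y + d·g and VDP is x + e·g, where x and y are standardised within scanner and have correlation r. With k = p(1 − p), the pooled correlation is

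r_obs = (r + k·d·e) / √[(1 + k·d²)(1 + k·e²)]

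**Dilution only (e = 0).** Then r_obs = r / √(1 + k·d²). For p = 0.5, k = 0.25:
- d = 0.5: 1/√1.0625 = 0.970
- d = 1.0: 1/√1.25 = 0.894
- d = 1.5: 1/√1.5625 = 0.800

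A true r of 0.50 reads 0.485, 0.447 or 0.400. By the Fisher z approximation, power to detect r = 0.20 at n = 200 falls from 81.2% to 78.8%, 71.8% or 62.0%. With a 20/80 split the factors are milder: 0.981, 0.928 and 0.857.

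**Spurious correlation (true r = 0).** Then r_obs = k·d·e / √[(1 + k·d²)(1 + k·e²)]. Rejection at two-sided 5% is Φ(atanh(r)·√197 − 1.96) plus the opposite tail. For p = 0.5:

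| d | e | r_obs | Rejection, n = 200 |
|---|---|---|---|
| any | 0 | 0 | 5% |
| 0.5 | 0.5 | 0.0625/1.0625 = 0.059 | 13% |
| 1.0 | 0.5 | 0.125/√(1.25 × 1.0625) = 0.108 | 33% |
| 1.5 | 0.5 | 0.1875/√(1.5625 × 1.0625) = 0.146 | 54% |

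For the last row, atanh(0.1455) × 14.04 − 1.96 ≈ 0.10, and Φ(0.10) ≈ 0.54. With a 20/80 split and e = 0.5, r_obs is 0.038 at d = 0.5 (rejection 8%) and 0.073 at d = 1.0 (18%). The first row is the important limit: if VDP does not differ between the scanner groups, nothing is created.

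**Effect of a scanner term.** Simulation with 10,000 replicates, n = 200 and p = 0.5 compared the pooled correlation with the partial correlation given scanner:
- True r = 0.30, d = 1, e = 0: mean 0.268 pooled, 0.300 adjusted
- True r = 0, d = e = 0.5: rejection 12.9% pooled, 5.3% adjusted
- True r = 0, d = 1, e = 0.5: rejection 33.6% pooled, 4.9% adjusted

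**The case against.** The strongest reply is that every quantity driving the result is assumed. The protocol gives no offset between these two scanners, no split, and nothing that ties scanner choice to VDP. Posture, inhaled nitrogen volume and breath-hold manoeuvre are the same on both machines, the buildings are adjacent, and this is a single-centre exploratory study. For offsets up to 0.5 SD the dilution is 3% or less. Section 8 does not forbid an analysis by scanner, and such detail often sits in a separate statistical analysis plan. All of that stands as a limit on size. It does not remove the point: section 8 names the statistic, and its adjustment clause covers only the dyspnea and asthma-control regressions, where a scanner term would in any case have to earn entry by p-value.

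A reader might go further and infer that scanner use following calendar time is enough to create a correlation. It is not, because VDP must also differ between the scanner groups. The long study period (2013 to 2028), the choice of 129Xe and/or 3He and the three chest coils leave such a difference possible, but the protocol does not show one.

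A reader might also extend the point to spirometry, since section 4.1.3 allows a second device ("and/or nDD EasyOne Spirometer, nDD Medical Technologies Inc"). That extension is weak. Appendix I requires calibration at least on every visit day and applies ATS acceptability criteria, all testing is done in one laboratory, and the protocol supplies no basis for an offset. Keeping each participant on one spirometer would serve longitudinal change and would not address these cross-sectional correlations.

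**Conclusion.** The point holds for CT, as a cheap improvement to the analysis. The protocol allows two scanners, measures WA% once per participant, and specifies correlations with WA% without a scanner term.

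The size depends entirely on assumed values. Under a 50/50 split, loss is slight for an offset of 0.5 SD and reaches about 11% of the correlation at 1.0 SD and 20% at 1.5 SD. False-positive inflation arises only if WA% and VDP both differ by scanner, and it exceeds one half only near a 1.5 SD offset combined with a 0.5 SD difference in VDP. The documents do not support saying that the planned correlations are biased; they support saying that the plan as written could not show whether they are.

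**What to change.** In section 8, state that the CT scanner is recorded for each participant and that the correlations of VDP and TCV with WA% are reported in two forms: the unadjusted Pearson correlation, and the partial correlation given scanner (or the within-scanner correlations, pooled). Give 95% confidence intervals for both.

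The cost is one recorded item and about one degree of freedom; no CT procedure changes. There is one real drawback. If the scanner groups truly differ in disease, for example because scanner use happened to follow recruitment source, adjustment removes that genuine between-group part of the relation. This is why both results should be shown, with the scanner split and the WA% and VDP summaries by scanner so that a reader can judge the difference.

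A spirometer-adjusted correlation is at most an optional sensitivity analysis. No rule fixing one spirometer per participant is needed for this point.

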# 4.1.7. Sputum Induction

Induced sputum will be collected at Visit 1, 1c and optional annual in-person visits. Sputum induction is a relatively non-invasive method to obtain sputum for cell or fluid phase inflammatory indices, culture or cytology. It is performed with an aerosol of normal or hypertonic saline generated by an ultrasonic nebulizer. The test will be performed post-bronchodilator to reduce the risk of chest discomfort. Participants will inhale the nebulized saline for 7 minutes up to 3 times, and will attempt to cough up a sample of sputum after each nebulization. FEV1 will be assessed after each nebulization, and the test will be stopped if FEV1 falls by >20% or >0.2L. If FEV1 falls by >20% or >0.2L, salbutamol will be given and FEV1 will be monitored until it is within 5% of baseline. Samples will be analysed by study staff at Robarts Research Institute. Analysis will begin within 2 hours of sputum collection, and samples will be kept in the locked sputum lab until analysis is complete, at which time samples will be destroyed.

#### 4.1.8. Instruments

Participants with asthma will complete self-assessments in the form of the Asthma Quality of Life Questionnaire with Standardised Activities (AQLQ(S)) (bi-weekly) and Asthma Control Questionnaire (Appendix VI and VII). Self-reported data will be uploaded by each participant with asthma monthly to our website using a confidential and password protected upload (https://apilab.ca/patients.html). Participants will also complete the modified Borg Dyspnea Scale (Appendix VIII) and MRC Dyspnea scale (Appendix IX) at each visit to evaluate breathlessness at baseline and after therapy. Participants will complete the St George's Respiratory Questionnaire (SGRQ) at the time of their visit (Appendix X).

DATE: November 15, 2024

#### 4.2. Centers

This is a single center study conducted at Robarts Research Institute, The University of Western Ontario.

# 4.3. Number of Participants

200 Asthmatic male and female participants, as well as 30 healthy volunteers aged 18-85 will be used for this study.

# 5. PARTICIPANT SELECTION CRITERIA

Male and females aged 18-85 will be used for this study. Participants will be recruited through the Asthma Centre located at St. Joseph's Hospital as well as the site's established database of Asthma patients. The London City-Wide Respirology practice serves over 1000 asthma patients annually.

30 healthy volunteers will also be recruited. Volunteers will include males and females aged 18-85. Healthy volunteers will be recruited via flyer advertisement in the community.

30 participants with asthma will be recruited from [name] practice and research program at the Firestone Institute, McMaster University, and will be included in our 200 asthmatic male and female participants.

#### 5.1. Inclusion Criteria

- Participants male and female aged 18-85 with a clinical diagnosis of asthma
- Healthy participants male and female aged 18-85
- Asthmatic participants with smoking history ≤ 1 pack/year
- Participant understands the study procedures and is willing to participate in the study as indicated by signature on the informed consent
- Participant is judged to be in otherwise stable health on the basis of medical history
- Participant able to perform reproducible pulmonary function testing (i.e., the 3 best acceptable spirograms have FEV1 forced vital capacity (FVC) values that do not vary more than 5% of the largest value or more than 100 ml, whichever is greater.)
- FEV1 >60% predicted

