#### 4. EXPERIMENTAL DESIGN AND METHODS

# 4.1. Overall Design and Control Methods

In 200 asthma patients, we propose to apply Xe MR image acquisition and analysis methods in order to characterize and probe the relationship between lung structure and function using imaging.

The first 60 participants with asthma will also be asked to complete additional follow up visits at the clinic after 2, 4 and 78 weeks. These visits are detailed in the schedule below.

The 30 healthy volunteers will be asked to complete the same study procedures to allow for a comparison between the resting state brain activity as well as lung structure and function between those with and without asthma.

All participants will visit Robarts Research Institute according to the following schedule:

V1 Baseline	V1a* BL+14±2d	V1b* BL+28±2d	V2 Telephone/ optional In-person BL+52±2wk	V1c* BL+78±8wk	V3 Telephone/ optional In-person BL+104±8wk	V4-10 optional in- person annual visit
 Xe/  He MRI	 Xe/  He MRI	 Xe/  He MRI	 Xe/  He MRI	 Xe/  He MRI	 Xe/  He MRI	 Xe/  He MRI
Full PFT	Full PFT	Full PFT	Full PFT	Full PFT	Full PFT	Full PFT
MCh	Meds/Exac	Meds/Exac	Meds/Exac	Meds/Exac	Meds/Exac	Meds/Exac
FOT	FOT	FOT	FOT	FOT	FOT	FOT
FeNO	FeNO	FeNO	FeNO	FeNO	FeNO	FeNO
BORG	BORG	BORG	BORG	BORG	BORG	BORG
MRC	MRC	MRC	MRC	MRC	MRC	MRC
sputum			sputum	sputum	sputum	sputum
СТ						
RS-fMRI (if applicable)						

\*Applicable to only the first 60 participants with asthma.

DATE: November 15, 2024

All participants with asthma will also complete bi-weekly and weekly quality of life questionnaires. Self-reported data will be uploaded by each participant monthly to our website using a confidential and password protected upload.

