#### 5.2. Exclusion Criteria

- Participant is, in the opinion of the investigator, mentally or legally incapacitated, preventing informed consent from being obtained, or cannot read or understand the written material
- Participant is unable to perform spirometry or plethysmography maneuvers
- Healthy participants with a previous clinical diagnosis of respiratory disease, psychological disorder(s) or head trauma

DATE: November 15, 2024

- For the subset of asthmatics identified as underperceivers and undergoing brain fMRI, participants with a previous clinical diagnosis of psychological disorder(s) or head trauma
- Participant has an implanted mechanically, electrically or magnetically activated device or any metal in their body, which cannot be removed, including but not limited to pacemakers, neurostimulators, biostimulators, implanted insulin pumps, aneurysm clips, bioprosthesis, artificial limb, metallic fragment or foreign body, shunt, surgical staples (including clips or metallic sutures and/or ear implants.) (At the discretion of the MRI Technologist/3T Manager).
- In the investigator's opinion, participant suffers from any physical, psychological or other condition(s) that might prevent performance of the MRI, such as severe claustrophobia.
- Patient is pregnant
- Healthy participants with a previous clinical diagnosis of a respiratory disease or a history of head trauma or psychological disorders that may affect the ability to participate or follow instructions during the MRI. The healthy volunteer has to be a never smoker.

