# 6. STUDY PROCEDURES

# 6.1. Screening Procedures for Study Entry

Eligibility for this study will be determined by the participant's clinical history, including respiratory disease and medication history. In addition, the investigator or designate shall discuss with each participant the nature of the study, its requirements and its restrictions, and an informed consent document will be signed. Each participant will be assigned a unique Study Number that will serve to identify participant study documentation. If a participant fails to qualify for enrollment, his/her Study Number may not be reused for another participant.

Participants performing fMRI will be either healthy volunteers or have been identified as having poor asthma control and demonstrate inaccurate perception of their asthma symptoms using asthma control and quality of life questionnaires. Specifically, these asthmatic participants are unable to sense sensations of dyspnea during asthma flair-ups. Participants who have suffered from a brain or head injury or participants that have diagnosed with an anxiety and depression disorder will be excluded from this part of the study.

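### Healthy volunteers face no lung-function limit stricter than the common FEV1 >60% predicted, so a never smoker with unrecognised airflow obstruction can enter as a control for the lung comparison

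*Protocol*

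**What the plan says.** Protocol section 5.1 is a single list for both groups. Lines meant for one group name it: "Healthy participants male and female aged 18-85" for the volunteers, and "Asthmatic participants with smoking history ≤ 1 pack/year" for the patients. The spirometric line, "FEV1 >60% predicted", names neither. The list also asks for reproducible spirometry, but that concerns the quality of the test and not the level of lung function.

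Section 5.2 excludes "Healthy participants with a previous clinical diagnosis of respiratory disease, psychological disorder(s) or head trauma" and adds "The healthy volunteer has to be a never smoker". Section 6.1 opens with "Eligibility for this study will be determined by the participant's clinical history", and section 5 states that "Healthy volunteers will be recruited via flyer advertisement in the community".

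Section 4.1 has the volunteers follow the same procedures as the patients "to allow for a comparison between the resting state brain activity as well as lung structure and function between those with and without asthma". Section 4.3 gives 200 asthmatic participants and 30 healthy volunteers. Full pulmonary function tests are scheduled at Visit 1 (section 4.1) and are done in all participants (section 4.1.3). No section uses the result to confirm that a healthy volunteer's lung function is normal.

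**The concern.** A healthy control group for a lung study should be free of the abnormality under study. Here the only limit on the level of lung function is the floor shared with the patients, and everything else rests on what is already known from history. Unrecognised airflow obstruction is by definition absent from the history.

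With 30 controls, a few such volunteers carry weight. They would move the control mean of VDP, oscillometry or spirometry towards the asthma mean and widen the control distribution. Both effects make a true asthma-healthy difference in lung measures harder to see. The study already collects the measurement that would prevent this.

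**Working it through.** **Step 1: which written rules a volunteer must pass.** Take a never smoker of any age from 18 to 85, with no respiratory diagnosis and an FEV1 of 65% predicted.

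- Age range (5.1): passes.
- FEV1 line (5.1), read as applying to everyone: 65 > 60, passes.
- FEV1 line, read as meant for patients only: no limit applies, passes.
- Stable health by history (5.1): passes if nothing is known.
- No previous respiratory diagnosis (5.2): passes.
- Never smoker (5.2): passes.
- Review of clinical history, including respiratory disease and medication (6.1): nothing to find, passes.

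Both readings of the FEV1 line leave the same gap. No section requires a normal FEV1 or sets an FEV1/FVC limit for volunteers.

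**Step 2: direction and possible size for a lung measure.** The protocol has no figure to reproduce. All values here are assumptions: normal VDP 2% with SD 1, and VDP 10% in an obstructed volunteer with the same within-type SD. With a share q of the 30 controls obstructed:

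- control mean = 2 + 8q
- control SD = √(1 + 64q(1 − q))

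| Obstructed of 30 | q | Mean (%) | SD |
|---|---|---|---|
| 0 | 0 | 2.00 | 1.00 |
| 1 | 0.033 | 2.27 | 1.75 |
| 2 | 0.067 | 2.53 | 2.23 |
| 3 | 0.100 | 2.80 | 2.60 |

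The relative shrinkage of the asthma-healthy difference is 8q/(A − 2), where A is the asthma mean VDP. The protocol does not give A. For one to three obstructed controls:

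- A = 5%: 0.267/3 to 0.8/3, or 9% to 27%
- A = 10%: 0.267/8 to 0.8/8, or 3.3% to 10%
- A = 20%: 0.267/18 to 0.8/18, or 1.5% to 4.4%

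**Step 3: effect on power, if such controls resemble asthmatics.** Assume a two-sided 5% test, SD 1 in both groups, 30 against 200, and an effect chosen to give 80% power with clean controls: √(1/30 + 1/200) × (1.960 + 0.842) = 0.55 SD. If c is the share of controls resembling asthmatics, the difference becomes 0.55(1 − c) and power is Φ(2.802(1 − c) − 1.960).

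- 1 of 30: 0.53 SD, power 77%
- 3 of 30: 0.49 SD, power 71%
- 6 of 30: 0.44 SD, power 61%

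This holds the SD at 1 and so leaves out the wider control spread shown in step 2.

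**Step 4: chance that at least one such volunteer enters.** With an assumed rate p among volunteers, the chance is 1 − (1 − p)^30: 45% for p = 2%, 79% for p = 5% and 96% for p = 10%.

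**The case against.** Four points can be made on the other side.

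- **Other safeguards exist.** A reader might infer that 60% predicted is all that a healthy volunteer needs. That is wrong. Never smoking, no previous respiratory diagnosis and stable health all apply, and the screening history covers medication. What remains is undiagnosed, unmedicated obstruction in a never smoker. This stands as a limit on how often the gap will matter, but it does not close the gap.
- **The planned tests are elsewhere.** The hypotheses in section 3 that name healthy volunteers concern BOLD and DTI, and section 8 names the healthy group only in the fMRI tests. No asthma-healthy test of VDP is specified. This stands: the lung comparison rests on the purpose stated in section 4.1. That purpose is explicit, however, and the volunteers are enrolled to serve it.
- **Carry-over to the brain contrasts is not shown.** A reader might infer that BOLD differences are also pulled towards zero. The protocol gives no figure linking FEV1 or VDP to BOLD, and it treats the link as a hypothesis. An undiagnosed volunteer need not resemble a poorly controlled underperceiver. The effect is possible, no more.
- **The study is exploratory and the data are on file.** Visit 1 spirometry makes the problem visible and partly recoverable, and a repeat analysis could sit in a statistical analysis plan. This limits the weight of the point. It does not remove it, because who may enrol as healthy is an eligibility rule fixed in this document.

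**Conclusion.** The point holds as a gap in the definition of the control group. The written rules admit a never smoker with unrecognised airflow obstruction as a healthy control for the lung comparison. The likely direction is smaller asthma-healthy differences in lung measures and a wider control spread.

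The size cannot be derived from the protocol. Every figure above rests on an assumed rate of obstruction, assumed VDP values or an assumed effect size. In particular, no single percentage loss can be quoted for group contrasts: for the same one to three volunteers it runs from 1.5% to 27% as the assumed asthma mean VDP goes from 20% down to 5%.

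A reader might also want to remove volunteers who react to methacholine. The protocol does not support that step. It defines no PC20 range for the purpose, and the rule would select on the response to the very challenge whose post-challenge BOLD contrast is tested.

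**What to change.** In section 5.1:

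1. State that the FEV1 limit of 60% predicted applies to asthmatic participants.
2. Add a criterion that healthy volunteers have baseline spirometry at Visit 1 within normal limits. One example is FEV1 at or above 80% predicted with FEV1/FVC at or above the lower limit of normal. These cut-offs are illustrative and not taken from the protocol; the sponsor should set and state the definition.

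For volunteers already enrolled, apply the same rule as a flag on their Visit 1 spirometry. Report how many are flagged, and repeat the lung comparison without them.

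The cost is a short eligibility amendment and a few extra screen failures among volunteers recruited by flyer. No new procedure is needed, since spirometry is already done at Visit 1.
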